## SCHEMA

## A5290

A Randomized, Phase 2b Study of a Double-Dose Lopinavir/Ritonavir Based Antiretroviral Regimen with Rifampin-Based Tuberculosis Treatment versus a Standard-Dose Lopinavir/Ritonavir Based Antiretroviral Regimen with Rifabutin-Based Tuberculosis Treatment with or without Raltegravir in HIV-1-Infected Persons Requiring Treatment for Active TB and HIV

DESIGN

A5290 is a prospective, randomized (1:1:1), open-label, phase 2b study comparing three lopinavir/ritonavir (LPV/r)-based antiretroviral (ARV) regimens among participants in high tuberculosis (TB) endemic resource-constrained settings undergoing treatment for confirmed or probable TB and requiring protease inhibitor (PI)-based antiretroviral therapy (ART). A two accrual period design will be used, including a full pharmacokinetic (PK) and safety evaluation to be conducted when 54-60 participants enrolled during the accrual period 1 have completed 28 days of ARV treatment and day  $12 \pm 2$  (after initiation of ART) drug levels are available (an early interim PK and safety evaluation will also be completed when 10-12 participants per arm have completed 28 days of ARV treatment and day  $12 \pm 2$  drug levels are available).

DURATION

Each participant will be followed until week 72.

SAMPLE SIZE

471 participants.

POPULATION

HIV-infected persons (male or female) at least 18 years of age with documented HIV infection, a clinical diagnosis of probable or confirmed active TB (including extrapulmonary TB) with susceptibility to rifampin (RIF), and who require a PI-based ARV regimen.

REGIMENS

Study-provided drugs include lopinavir/ritonavir (LPV/r), ritonavir (RTV), raltegravir (RAL), and rifabutin (RBT).

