The core team and SMC will then review the results of the second accrual period 1 interim PK and safety analysis. If acceptable PK criteria are not met, or if more than three participants in one or more treatment arms report ≥ Grade 3 AEs attributed to study-provided drug(s) by 28 days after initiation of ART, or if more than three participants in one or more treatment arms discontinue study-provided drug(s) for treatment-limiting toxicity or intolerance (such that PK assessments cannot be completed, then a decision will be made about whether to continue, modify (e.g., add additional participants to the accrual period 1 to assure adequate PK assessment are completed), or halt the treatment arm(s) in question, based on analysis of the nature of the AEs and reasons for study-provided drug discontinuation, and the degree of PK criteria failure. At the second interim review, if three or fewer participants report ≥ Grade 3 AEs attributed to study-provided drug(s) in all treatment arms, and if three or fewer participants in all treatment arms discontinue study-provided drug(s) for treatment-limiting toxicity or intolerance (such that PK assessments cannot be completed), and acceptable PK criteria are met for at least two of the treatment arms, the SMC, in consultation with the core team, will determine whether accrual period 2 will open.

If, based on the SMC's determination, unacceptable PK and/or safety criteria are met within two treatment arms, then further enrollment into the study may be stopped, and accrual period 1 participants will be managed according to best available local TB and ARV treatment. These participants will be followed off study-provided drug (LPV/r, RTV, RAL, and/or RBT) for the remainder of study follow-up (up to 72 weeks).

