Confirmed extrapulmonary TB is defined as the presence of compatible clinical symptoms as previously described plus clinical features of organs involved, such as sterile pyuria or other renal involvement, pericarditis, ascites, pleural effusion, meningitis, arthritis, orchitis, enteritis, extrathoracic lymphadenitis, or osteitis and positive culture for MTB or nucleic acid amplification test positive for MTB or MTB Complex from fluid or tissue biopsies from any of these organ or tissue sites, including bone marrow, liver, and blood.

Probable Pulmonary TB is based on the clinician's judgment and includes compatible clinical symptoms as previously described, and at least one of the following: 1) positive sputum smear for acid fast bacilli (AFB); or 2) abnormal CXR, chest CT scan or other chest imaging; or 3) evidence of granulomata with organisms positive for AFB or caseating granulomata on lung tissue biopsy; or 4) positive tuberculin skin test (TST) ( $\geq$  5mm) or interferon gamma release assay (IGRA); and without concurrent illness that would explain the findings, but MTB cultures are negative or not available.

Probable Extrapulmonary TB is based on the clinician's judgment and includes compatible clinical symptoms as previously described plus clinical features of organs involved as previously described, or evidence of granulomata with organisms positive for AFB or caseating granulomata on tissue biopsy from relevant site(s); and specific antituberculous therapy initiated or recommended, but MTB cultures are negative or not available.

NOTE: Participants whose qualifying episode of TB was later determined not to be TB will continue to be followed on study but off study drugs for safety and ART endpoints.

- 4.1.4 Chest x-ray within 30 days prior to study entry.
- 4.1.5 A PI-based ART regimen is required, as determined by the participant's primary clinician/clinical facility.

NOTE: Enter the reason, in the eligibility checklist, for the PI-based ART regimen from among the following choices:

The PI-based therapy was required:

- 1) Because the participant failed an NNRTI regimen or;
- 2) Because the participant had an adverse reaction to an NNRTI regimen or;
- 3) Because the participant received single dose nevirapine during pregnancy and could have NNRTI resistance mutations archived at the time the participant was starting ART;
- 4) Other, specify.

4.1.6 Laboratory values obtained within 14 days prior to study entry:

Accrual period 1

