**Premature ARV and/or TB Treatment and Premature Discontinuation Evaluations**

Participants who prematurely discontinue from the study, and participants who prematurely discontinue ARV and/or TB treatment, will have the discontinuation evaluations performed as noted in the SOE within 4 weeks after the discontinuation. If the participant discontinues any study-provided ARV, he/she will continue on the remaining study-provided ARVs and the date of the discontinuation of any study-provided (or study treatment) ARV drug and reason for discontinuation will be entered on the Antiretroviral Regimen Record. If the participant discontinues any study-provided TB drug, he/she will continue on the remaining TB drugs and the date of the discontinuation of the study-provided (or study treatment) TB drug and the reason for discontinuation will be entered on the TB Treatment Record.

When the participant takes the last dose of the last study-provided (or study treatment) drug (ARV and/or TB drugs), the Permanent Discontinuation of Study Drugs form will be completed with the date of study drug discontinuation and the reason for discontinuation. If the participant discontinues all study-provided (or study treatment) ARV or TB drugs prematurely, he/she will be encouraged to continue on study, off study treatment, and receive all evaluations as per the SOE through week 72.

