#### Entry and Subsequent Sputum Collections

At entry (not required if obtained within 3 days prior to entry), week 8, week 12, and at the time of suspected TB treatment failure/TB recurrence, participants will be given sterile collection containers to collect first morning expectorated sputum the day of their clinic visit. These specimens will be collected by induction if they cannot be spontaneously produced.

Sputum will be collected as described below:

- If the final dose of intensive phase of INH, RIF or RBT, EMB and PZA coincides with the week 8 visit, collect sputum samples within 72 hours of ingestion of the final dose of intensive phase of TB treatment and prior to the ingestion of the second dose of continuation phase TB medications.
- If the final dose of intensive phase INH, RIF or RBT, EMB and PZA does NOT coincide with the week 8 visit, (a) collect a sputum sample at week 8, and (b) schedule a separate visit within 72 hours of ingestion of the final dose of intensive phase of TB treatment and prior to the ingestion of the second dose of continuation phase TB medications.

- From week 16 onward, collect single sputum samples every 4 weeks (monthly) for smear and cultures if sputum culture results have not demonstrated two consecutive TB-negative cultures after week 12, and discontinue monthly smear and cultures once there are two consecutive TB-negative sputum cultures. Drug susceptibility testing on available samples should be done if the sputum culture remains MTB positive after the week 8 timepoint.

If the sputum sample does not become TB-negative by the week 16 time point, the participant has failed TB treatment. The participant will be taken off study TB medications and will be treated for possible drug-resistant TB at the discretion of the primary clinician according to local, national, or international guidelines used for treatment of drug-resistant TB. These participants will be followed on study, but off study-provided TB drugs until week 72. If the participant must discontinue study-provided TB treatment, he/she may still continue to take study-provided ARVs.

Collect sputum in a sterile single-use collection container. If possible, the oral cavity should be rinsed with clean water that is expectorated prior to giving the sample. The specimen should contain 3-5 mL of sputum.

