#### TB Evaluations

A review of all reported results from evaluations for the qualifying episode of TB performed at the local clinical or TB program site must be completed for all participants. At each visit, all diagnostic, laboratory and radiology results, and treatment information available regarding the qualifying (current) episode of TB, including any that is provided by the local TB clinic, must be recorded on the CRFs when received. This will include TB-related radiologic results, including most recent chest x-ray, AFB smear and culture results, and other evaluations related to TB diagnosis and evaluation of TB status. Any changes in results from repeated radiologic evaluations must be documented.

Participants whose qualifying episode of TB is later identified as drug-resistant according to the inclusion and exclusion criteria in section 4.0 will be discontinued from the study and referred to their primary clinician/clinical facility or TB and ART program and treated with the best available TB and ART according to local standards of care. Sites must notify the A5290 core team by e-mail ([[contact]](mailto:[contact])) within 2 weeks after learning that the participant's TB has been identified as drug-resistant.

Participants whose qualifying episode of TB was later deemed to be not TB will continue to be followed on study, off study-provided TB treatment, but on study-provided ART, for safety and ART endpoints.

Cultures from study samples identified as TB-positive, including any sample that is positive for drug-resistance, must be stored at the site laboratory or the local TB laboratory performing the TB testing (as appropriate to site procedures).

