## 7.2 Specific Management of Toxicities Related to Study-Provided Drugs

### 7.2.1 AST and ALT Elevation

ARVs, INH, RIF, RBT, and PZA can all cause alterations in liver function tests. Concomitant illnesses, including TB, may also alter these laboratory parameters. Therefore, changes in AST or ALT should be evaluated within the clinical context of the abnormalities.

Participants entering this trial will potentially have advanced HIV disease and active TB. Elevation in ALT and AST is expected. Because this study is designed to assess the risk/benefit ratio of second-line ART with varying doses of LPV/r

and RBT as an alternative for RIF in this population, participants with  $\leq 2 \times$  ULN for ALT will be allowed to enroll in accrual period 1 and participants with  $\leq 5 \times$  ULN for both parameters will be allowed to enroll in accrual period 2 of the study. If the AST or ALT elevation is considered most likely to be due to concomitant illness or medication, standard management, including discontinuation of the likely causative agent, should be undertaken.

For asymptomatic or symptomatic elevation of AST or ALT  $> 7.5 \times$  ULN (Grade 3), all medications should be discontinued and held until levels and symptoms are Grade  $\leq 2$ , at which time therapy may be reintroduced. All medications may be restarted if the laboratory abnormalities were thought secondary to a concomitant illness.

If the elevation of AST or ALT is thought to be due to RBT, anti-TB medications should be reintroduced one at a time in 3-7 day increments, and if all other anti-TB medications are tolerated, RBT should be added last, initially at a reduced dose according to Table 5.1. If the participant was already receiving RBT at a reduced-dose then the re-challenge dose should be the dose the participant was previously receiving. If the RBT dose is tolerated upon re-challenge for 7 days, then the ARVs should be restarted. If Grade 3 or higher elevation of AST or ALT recurs with the reintroduction of RBT then RBT should be permanently discontinued and the participant should be referred to his/her primary clinician or local TB program, provided the best available anti-TB therapy according to local standards, and the participant should continue to be followed on study but off study-provided anti-TB medications.

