The core team and SMC will then review the results of the second accrual period 1 interim PK and safety analysis. If acceptable PK criteria are not met, or if more than three participants in one or more treatment arms report  $\geq$  Grade 3 AEs attributed to study-provided drug(s) by 28 days of ART, or if more than three participants in one or more treatment arms discontinue study-provided drug(s) for treatment-limiting toxicity or intolerance (such that PK assessments cannot be completed), then a decision will be made about whether to continue, modify (e.g., add additional participants in the accrual period 1 to assure adequate PK assessment are completed), or halt the treatment arm(s) in question, based on analysis of the nature of the AEs and reasons for study-provided drug discontinuation, and the degree of PK criteria failure. At this second interim review, if three or fewer participants report  $\geq$  Grade 3 AEs attributed to study-provided drug(s), and if three or fewer participants discontinue study-provided drug(s) for treatment-limiting toxicity or intolerance (such that PK assessments cannot be completed), and if acceptable PK criteria are met for at least two of the treatment arms, the SMC, in consultation with the core team, will determine whether accrual period 2 will open.

If, based on the SMC's determination, unacceptable PK and/or safety criteria are met within two treatment arms, then further enrollment into the study may be stopped, and accrual period 1 participants will be managed according to best available local TB and ARV treatment. These participants will be followed off study drug for the remainder of study follow-up (up to 72 weeks).

If the SMC determines that accrual period 2 enrollment should proceed, accrual period 2 participants will then be randomized 1:1:1 to Arm A, B, or C (or with

equal probability to the remaining sample size in the remaining treatment arms) at the doses determined during the dose-finding period in accrual period 1 participants. No individual dose adjustments will be made based on drug concentrations for participants enrolled during the accrual period 2.

Based on this monitoring, if criteria are determined to be unacceptable in any treatment arm before the three accrual period 1 cohorts are fully enrolled, further accrual to the arm in question may be stopped.

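### Protocol 4.1.3 takes participants later found not to have TB off study drugs, which here include the ART, while 6.3.5 keeps them on study ART

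*Protocol*

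**What the plan says.** Two current passages of the protocol cover the same event, a qualifying TB episode that is later judged not to be TB.

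- Section 4.1.3, NOTE after the TB case definitions: these participants "will continue to be followed on study but off study drugs for safety and ART endpoints".
- Section 6.3.5, TB Evaluations: they "will continue to be followed on study, off study-provided TB treatment, but on study-provided ART, for safety and ART endpoints".

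The clarification memo of 18 April 2013 alters neither sentence. It deals with Note A in 4.2.3, the medication history table in 6.3.4, the accrual text in 9.4.3 and the references to the FDA.

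Section 8.2 lists a finding of not TB among the reasons for permanently stopping TB treatment. The matching list for antiretrovirals in 8.1 does not include it. Neither section says outright that ART continues.

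**The concern.** The population, the trigger and the stated purpose of follow-up are the same in both sentences. Only the treatment instruction differs, and the difference is whether HIV therapy is stopped. A site working from the eligibility section could withdraw study-provided ART, and a site working from 6.3.5 would continue it.

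Every participant enters because a clinician has decided that a PI-based regimen is required (4.1.5). The NOTE in 8.1 requires referral for best available ART when study antiretrovirals are permanently stopped, so a participant taken off study ART need not go untreated. That participant would still leave the randomised regimen for a reason unrelated to toxicity, efficacy or choice. Section 9.6.2 keeps all enrolled participants in the analysis of the overall objectives, so inconsistent handling would feed into the arm comparisons. It could also enter the SAP section 4.2 tables, which count discontinuations of study-provided drugs by arm within and beyond 28 days.

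The situation is foreseeable. Section 4.1.3 admits probable TB on clinical judgment, with cultures negative or unavailable, and the protocol provides for a later finding of not TB in three places (4.1.3, 6.3.5 and 8.2).

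**Working it through.** No calculation decides this point. The question is whether study drugs, as this protocol uses the term, could mean the TB drugs alone. If so, the two sentences agree; if not, they conflict. The glossary has no entry for the term, so usage has to settle it.

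**Uses that show what the term covers**

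1. Schema, Regimens: "Study-provided drugs include lopinavir/ritonavir (LPV/r), ritonavir (RTV), raltegravir (RAL), and rifabutin (RBT"). Three of the four are antiretrovirals and one, rifabutin, is a TB drug.
2. Section 6.2.7, on what a site records at the end of treatment: "last study-provided (or study treatment) drug (ARV and/or TB drugs), the Permanent Discontinuation of Study Drugs form will be completed". The form's title uses study drugs for both classes.
3. Section 6.3.5, on treatment modifications, applies study drug to antiretrovirals and anti-TB agents together.
4. Sections 3.0 and 9.5.1 give one instruction for the case where two arms fail the interim criteria. Section 3.0 spells it out: "These participants will be followed off study-provided drug (LPV/r, RTV, RAL, and/or RBT) for the remainder of study follow-up". Section 9.5.1 shortens it: "These participants will be followed off study drug for the remainder of study follow-up". The short form stands for a list that includes the ART.

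**How the protocol writes it when only TB drugs stop**

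5. Section 6.3.2, after TB treatment failure: "These participants will be followed on study, but off study-provided TB drugs until week 72".
6. Section 7.2.1, after recurrent transaminase elevation on rifabutin: "the participant should continue to be followed on study but off study-provided anti-TB medications".

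In items 5 and 6 the drug class is named. The 4.1.3 NOTE names no class.

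**Result.** All four uses in items 1 to 4 include the antiretrovirals. With that meaning, the NOTE says to stop study ART and 6.3.5 says to continue it, so the sentences conflict.

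**Number who could be exposed.** SAP 1.6 states that accrual period 2 will not open. Accrual period 1 was planned at 20 per arm (protocol 3.0; SAP 1.3):

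- 20 × 3 = 60 participants
- 60 / 471 = 12.7% of planned enrolment

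This is the planned group within which a not-TB finding could arise. It is not the share affected, and neither document gives a figure for that share.

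**The case against.** The best counter-argument is that the protocol's terms are loose and the intent is clear from elsewhere.

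*Loose wording.* Section 7.1 (Grade 4) describes follow-up off study-provided medications after permanent discontinuation of ARV or TB drugs. Section 6.2.7 speaks of being off study treatment when all drugs of either class are stopped. Both can be read as general phrases triggered by one class alone, so the protocol does not always name the class. This stands, and it weakens the contrast drawn from items 5 and 6. Both passages can also be read as stopping everything, however, and neither uses study drugs in a sense that excludes the ART.

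*Clear intent.* The NOTE sits under the TB criterion and closes with the same purpose clause as 6.3.5. Section 6.3.5 is the operational section and is explicit. A site stopping ART on the strength of the NOTE would find no matching reason in 8.1. In the setting of TB treatment failure, 6.3.2 allows study ARVs to continue after study TB treatment stops. This also stands, and a careful reader would probably continue ART. It shows which sentence is wrong. It does not remove the other one: the NOTE has no cross-reference to 6.3.5, and no rule says which takes precedence.

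*Small consequence.* Nothing in the documents shows that any site acted on the NOTE. Keeping such participants in the analysis is ordinary intention-to-treat practice. The SAP supplied covers the interim PK and safety report and has no week-48 virologic section. All of this is accepted, and it limits the weight of the point.

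**Conclusion.** The concern holds. The 4.1.3 NOTE is wrong as written: taken literally, it ends randomised LPV/r, and raltegravir in Arm C, for participants whom 6.3.5 keeps on those drugs.

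The effect is low and unquantified. It depends on how many accrual period 1 participants were found not to have TB and on which sentence their site followed, and the documents give neither. No loss of power is claimed. The textual conflict is certain. That sites actually handled participants differently is a possibility, not a finding.

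The conclusion assumes that study drugs in the NOTE means what it means in 3.0, 6.2.7, 6.3.5 and 9.5.1. It is worth correcting despite its size, because the sentence is a treatment instruction and not background text.

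**What to change.** By clarification memo, replace the end of the 4.1.3 NOTE with the 6.3.5 wording, so that these participants "will continue to be followed on study, off study-provided TB treatment, but on study-provided ART, for safety and ART endpoints". The 2013 memo already corrected an eligibility note in this way (4.2.3, Note A). If follow-up has finished, the study report should instead state how any such participants were handled and whether study ART was stopped.

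The cost is one sentence in a memo, with no change to design, sample size or analysis.

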#### 4.2 Exclusion Criteria

- 4.2.1 History of completed TB treatment and resolution of TB symptoms less than 1 year prior to the current TB episode at study entry, or incomplete treatment for a prior episode of TB (i.e., defaulted past TB treatment) at any time prior to the current TB episode.

NOTE: Completed TB treatment is defined as completion of an 8-week intensive phase of TB treatment with INH and RIF plus at least 2 other anti-TB drugs, followed by a 16-week continuation phase of TB treatment with INH and RIF for a total duration of at least 24 weeks of TB treatment.

- 4.2.2 Documented multidrug-resistant tuberculosis (MDR TB) or extensively drug-resistant (XDR) TB.

NOTE: MDR TB is defined as TB with resistance to RIF and INH. XDR TB is defined as MDR TB plus resistance to fluoroquinolones and to at least one second-line injectable anti-TB drug. If MDR TB or XDR TB is determined based on locally-obtained drug susceptibility testing after study entry, the participants will be discontinued from the study and referred to their primary clinician/clinical facility or TB and ART program and treated with the best available TB and ART according to local standards of care.

- 4.2.3 Participants infected with a rifamycin resistant strain of TB as determined by HAIN GenoType MTBDR Plus line probe assay or, GeneXpert® MTB/RIF assay (or, following approval of the core team, a result from another locally-obtained standardized RIF drug susceptibility test). Participants found to have a rifamycin-resistant strain of TB should be referred for management according to the site's standard of care.

NOTE A: Participants may be enrolled pending the results of RIF drug susceptibility testing if a rapid HAIN GenoType MTBDR Plus line probe

assay, GeneXpert® MTB/RIF assay, or other rapid MTB RIF drug resistance assay result is not yet available. However, if RIF drug-susceptibility test results are not available within 60 days after study entry or if any drug susceptibility testing subsequently demonstrates RIF resistance, participants will be discontinued from the study and referred to their primary clinician/clinical facility or TB and ART program and treated with the best available TB and ART according to local standards of care.

NOTE B: All specimens available from participants at entry should also be tested for INH drug susceptibility (as per the SOE and section 6.3.2), however, INH monoresistance (i.e., the baseline isolate is resistant only to INH) is not an exclusion criterion for enrollment. If the HAIN GenoType MTBDR Plus line probe assay is used or if any other rapid drug susceptibility test is used that also supplies information on INH susceptibility, these results will be recorded. If a GeneXpert MTB/RIF assay is used, which only detects RIF resistance, then samples should also be tested with another standardized method that also evaluates INH susceptibility.

4.2.4 Receipt of more than 28 cumulative days of anti-TB treatment for the current TB episode prior to study entry.

NOTE: Receipt of therapy for latent TB is permitted as is receipt of short-term augmentin or a fluoroquinolone (for < 14 days) for treatment of bacterial infections.

4.2.5 Active drug or alcohol use or dependence that, in the opinion of the site investigator, would interfere with adherence to study requirements.

4.2.6 Active illness requiring systemic treatment and/or hospitalization within 30 days prior to study entry, or that in the opinion of the site investigator, might otherwise interfere with adherence to study requirements.

4.2.7 Pregnant or breastfeeding.

4.2.8 Anticipated receipt of any of the prohibited medications listed in section 5.4.2.

4.2.9 Known intolerance/allergy/sensitivity or any hypersensitivity to components of study drugs or their formulations.

4.2.10 History of close contact with known MDR or XDR TB patients at any time prior to study entry.

NOTE: Close contact is defined as participant history of prolonged, frequent, or intense contact approximating > 8 hours per day with a person known to have infectious MDR or XDR TB e.g., household, other congregate living or incarceration contacts.

